4.7. Disposition of patients

The number of patients screened, the number of patients randomized and the number of patients in each analysis population will be summarized. The reasons for exclusion from each analysis population will be summarized for all patients randomized. The reasons for non-eligibility for randomization, i.e. the violated inclusion or exclusion criteria will be listed for all non-randomized patients by visit.

Major protocol deviations (leading to the exclusion from the PP) and minor protocol deviations (not leading to the exclusion from the PP) will be summarized for the safety population. The determination of major and minor protocol deviations will be performed during the blind data

review meeting documented in the blind data review meeting minutes, which will be finalized prior to unblinding of the treatment group for the main analysis of data of the double-blind treatment.

The number of patients who completed the study and the number of patients who terminated the study early will be summarized in frequency tables for the safety, the FAS, the ITT and the PP populations.

The timing of early termination will be summarized for each study month for the safety, the FAS, the ITT and the PP populations.

Consolidated Standards of Reporting Trials (CONSORT) diagram (Moher et al. 2001) will be used to present abovementioned data in a graphical form.

4.8. Demographic and baseline variables

Demographic data and other baseline characteristics will be summarized for Safety, FAS, ITT and PP population by treatment group and overall. Separate tables for Safety and ITT populations will be prepared when number of patients in those populations will differ from FAS population. The following variables will be summarized:

- Age (years) as continuous variable [(date of ICF signature – date of birth)/365.25]
- Age category (<57/ ≥57 years old)
- Sex (male / female)
- Race
- Weight [kg] and height [cm]
- BMI [kg/m²] calculated as Weight (kg)/[height (m)²]
- BMI categories (Underweight/ Normal weight/ Overweight/ Obese)
- History of plasma donation (yes / no)
- History of blood donation (yes / no)
- Use of special diet (yes / no)

A separate table will summarize a history of alcohol and drug abuse and substance use history:

- History of alcohol abuse (yes / no)
- History of drug abuse (yes / no)
- Smoking (Never, Current, Former, Not collected)
- Amount of cigarettes smoked [pack-years]
- Amount of coffee consumed [cups]
- Amount of tea consumed [cups]
- Amount of energy drinks consumed [cans].

Disease characteristic will summarize:

- Duration of rheumatoid arthritis (years)
- Duration of methotrexate treatment (years)
- Tender (68) and swollen (66) joints
- DAS28-CRP assessment from screening and Day 1 baseline including disease activity categorization.

A separate table will summarize results on rheumatoid biomarkers indicators collected during screening and Day 1 baseline.

Total scores, collected during baseline, will be summarized in a table for following scales:

- Physician Global Assessment of Arthritis (PhGA)
- Patient's Global Assessment of Arthritis (PtGA)
- Patient Assessment of Arthritis Pain (PAAP)
- Health Assessment Questionnaire – Disability Index (HAQ-DI) including pain level measured with VAS.

Due to size a separate table will present subscales of 36-Item Short Form Survey Instrument (SF-36) and total score from Functional Assessment of Chronic Illness Therapy – Fatigue (FACIT-F).

Separate tables will be produced for screening and baseline safety data:

- Vital signs: blood pressure [mmHg], heart rate [beats per minute], body temperature [°C] (numerical results as well as categorization of result)
- 12-lead ECG results: ECG finding, QTc Value (in ms), QRS value (in ms) – with the former two parameters presented as an average of up to three measurements at screening and one measurement thereafter).
- Physical examination (combining results from screening and baseline – in case of new abnormalities observed on Day 1, worst case will be presented in table).

Additional tables will be prepared for history of vaccination and viral serology at screening.

Other baseline characteristics will be listed only as applicable showing results for patients with abnormal results at screening or baseline.

All other screening or Day 1 safety assessments will be listed only unless specified differently below.

4.9. Medical history

Current medical conditions are defined as those entries in medical history that are ongoing at the screening visit. Medical histories and current medical conditions will be coded using a MedDRA dictionary (version of MedDRA current at the time of database lock will be used). Medical histories and current medical conditions will be summarized by treatment group and overall for the full analysis set.

Reproductive history will be listed only.

4.10. Concomitant medication

Prior and concomitant medications will be classified using information on ATC codes contained in Register of Medicinal Products Approved for Marketing on the territory of the Republic of Poland¹. Summary of concomitant medications will be provided as count and frequency for ATC level 2 (therapeutic subgroup) and 4 (chemical subgroup). Listings of prior and concomitant medications will be provided and sorted by site, patient number, name of active substance, and date of last administration (if known). Data on methotrexate administration will be presented only in form of listing. Rescue medications will be presented in form of listing (if applicable). Information on prior use of following drug classes: glucocorticosteroids, NSAIDS

¹ <https://rejestrymedyczne.ezdrowie.gov.pl/rpl/search/public>
03JAK2021

and DMARDs and will be presented as number and frequency of subjects using each class of these drugs (see 4.2.16 for definition).

4.11. Efficacy analyses

Unless otherwise specified all efficacy analyses will be performed on ITT data with sensitivity analyses performed on PP population and ITT population with data imputed using methods described in section 4.6. In addition, efficacy analyses will be performed in subgroups defined in section 3.2.

4.11.1. Primary efficacy endpoints

The main analysis will be based on ITT population with supportive analyses using PP population data and imputed ITT population as sensitivity analysis.

In order to evaluate clinical efficacy of CPL409116 at week 12 in subjects with active RA who have had an inadequate response to methotrexate a Mixed Model for Repeated Measure (MMRM) will be prepared.

A set of hypotheses (H_0 – null and H_A – alternative) will be tested, one for each dose level of CPL409116.

H_01 : The mean change at week 12 from baseline in CPL409116 at dose of 60 mg BID is the same as that observed in placebo arm.

H_A1 : The mean change at week 12 from baseline in CPL409116 at dose of 60 mg BID is different from that observed in the placebo arm.

H_02 : The mean change at week 12 from baseline in CPL409116 at dose of 120 mg BID is the same as that observed in placebo arm.

H_A2 : The mean change at week 12 from baseline in CPL409116 at dose of 120 mg BID is different from that observed in the placebo arm.

H_03 : The mean change at week 12 from baseline in CPL409116 at dose of 240 mg BID is the same as that observed in placebo arm.

H_A3 : The mean change at week 12 from baseline in CPL409116 at dose of 240 mg BID is different from that observed in the placebo arm.

These hypotheses will be tested using a 2-sided 5% significance level. No adjustment for multiplicity will be performed for comparisons of each concentration of CPL409116 to placebo at week 12.

Primary endpoint, change from Baseline in Disease Activity Score DAS28-CRP at Week 12, will be analyzed by MMRM model with factors for dose (placebo, 60 mg, 120 mg, 240 mg), timepoint (all measurements throughout the study will be taken into account, week 4, week 8, week 12, week 16), interaction between treatment and timepoint, clinical site, as well as baseline value of DAS28-CRP as continuous covariate. Subject will be treated as a random effect, with an unstructured covariance structure to account for the correlation among repeated measurements. If the model does not converge, another covariance structure, (e.g., AR(1), CS, etc.) will be explored. Missing data will be assumed to be missing at random. R formula which could be used for such analysis:

$$mmrm(CHANGE \sim TREATMENT * TIMEPOINT + AGE + SEX + SITE + BASELINE + us(VISIT|ID))$$

using *mmrm* function from *mmrm* library.

Pearson residuals will be used to identifying outlying observations and the appropriateness of the covariance structure. Normalized or scaled residuals will be used to check for normality and will be assessed graphically. Residuals from the primary model will be plotted against the predicted values and a quantile-quantile (QQ)-plot of the residuals versus the expected quantiles of the standard normal distribution will be presented.

The statistical model will allow for comparison of efficacy between placebo and 60 mg, 120 mg and 240 mg of CPL409116 at each of the timepoint. In order to compare each concentration of CPL409116 to placebo, LS means, their 95% CI, and p values will be calculated using *emmeans* function of *emmeans* library. Cohen's D effect size will be calculated as difference between means of given treatment arm and placebo and divided by pooled standard deviation.

Change from baseline in DAS28-CRP score at week 4, 8 and 16 will be analyzed on basis of LS-means calculated by MRMM model used in primary endpoint analysis also without adjustment for multiplicity.

Supportive analysis will be performed on PP population, as well as ITT with imputation based on last observation carried forward (LOCF) method and performed as described for the ITT population.

Sensitivity analysis of primary endpoint will include MMRM model with pooled CPL409116 arms and performed as described for the primary endpoint analysis. The only difference is that at each timepoint there will only be comparison between pooled CPL409116 and placebo. In addition, different formulation of the models will be explored (interactions between independent variables, simpler versions of the model).

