Statistical Methods	
Statistic Considerations
 
Following assumptions have been made for the purpose of sample size determination:
 

■ CPL409116 molecule study will be based on four parallel study arms (placebo and three increasing doses of CPL409116);

■ No interim analyses for efficacy are planned;

■ Subject with active rheumatoid arthritis (Baseline DAS28>3.2)

■ Study is performed in a multiple clinical sites;

■ Primary objective is considered: Change from Baseline in Disease Activity Score (DAS)28-C Reactive protein (CRP) (Week 12);

■ The primary endpoint will be analyzed using a mixed effect repeated measures model (MRMM). However, to estimate sample size a simulation based on ANCOVA model was used. This should be more conservative (i.e. should underestimate statistical power) than MRMM but allows for more robust sample size estimation;

■ Analyses for each dose will take form of ANCOVA model with Baseline DAS28-CRP, clinical site (up to five sites were considered in simulation) and drug dose (encoded as levels 1-3) as independent variable;

■ for both endpoints a normal distribution of baseline and final values is assumed;

■ in the scenario single ANCOVA model will be performed at the end of the study. Study is successful if at least one

	
treatment arm is superior to placebo.
 
Eighty four subjects (21 per treatment group) are required to have a 80% chance of detecting, as significant at the 5% level, a mean change in DAS28-CRP of -1.8 provided that change no greater than -1.0 will be observed in placebo group with combined standard deviation of 1.1. With dropout of ~16% - 100 subjects should be recruited, which gives 25 subject in each treatment group.

--	--

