### **10.3. Evaluation of Efficacy**

#### **Primary endpoint analysis**

Primary endpoint is change from baseline in (DAS)28-C Reactive protein (CRP) score at 12 weeks.

Analysis will include data on all CPL409116 arms and placebo. The primary analysis will be conducted on ITT analysis set with analysis of PP subset being supplementary to the main analysis.

The null hypothesis is that there are no differences in the primary endpoint between either dose group compared to placebo, versus the alternative hypothesis, that at least 1 dose group is significantly different, using a 2-sided 5% significance level. The primary endpoint will be analyzed using a mixed effect repeated measures model (MRMM), with treatment, timepoint and clinical site as fixed effects and baseline score as a covariate. Subject will be treated as a random effect, with an unstructured covariance structure to account for the correlation among repeated measurements. If the model does not converge, another covariance structure, (e.g., AR(1), CS, etc.) will be explored. Missing data will be assumed to be missing at random. The primary analysis will compare each dose group with placebo at Week 12.

Missing values due to a patient dropping from the study for lack of efficacy or adverse event, will be handled by setting the (DAS)28-C Reactive protein (CRP) score to last observation carried forward (LOCF).

Sensitivity analysis of primary endpoint will include MRMM model with pooled CPL409116 arms vs placebo. Details of this and other sensitivity analyses of primary endpoint will be described in the SAP.

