#### **Secondary Endpoints Analyses**

Change from baseline in DAS28-CRP score at week 4, 8, 12 and 16 will be analyzed on basis of LS-means calculated by MRMM model used in primary endpoint analysis without adjustment for multiplicity.

Proportion of subjects with DAS28-CRP remission on Week 12 (score <2.6) in each study arm will be presented together with confidence intervals and p values calculated using proportion test (adjusted for multiple comparisons). A logistic regression model with baseline DAS28-CRP, treatment and clinical site as independent variables will be also prepared to explain occurrence of remission. Median time to remission will be estimated using Kaplan-Meier method.

ACR20, ACR 50, ACR 70, and ACR 90 responder rates on Weeks 8 and 12 will be presented descriptively. Differences between CPL409116 arms and placebo will be presented together with confidence intervals and p values calculated using proportion test (adjusted for multiple comparisons). Logistic regression models with baseline DAS28-CRP, treatment and clinical site as independent variables will be also prepared to explain achievement of response.

Change from baseline in the Tender/Painful and Swollen Joint Count (Weeks 8 and 12) and change from baseline in PhGA of Arthritis (Weeks 8 and 12) will be analyzed using MRMM models (using respective baseline values, dose and clinical site as fixed effects and subject as random effect. These analyses will be performed without adjustment for multiplicity.

Further details of secondary endpoints' analyses will be provided in the SAP.

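### The 5% that Protocol 10.3 attaches to finding at least one effective dose is about 12.5% under the SAP's three unadjusted tests; the SAP also drops the adjustment the Protocol promised for remission and ACR

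*SAP*

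**What the plan says.** **Primary endpoint.** Protocol 10.3 (Primary endpoint analysis) states a single null, that no dose group differs from placebo, against the alternative "that at least 1 dose group is significantly different, using a 2-sided 5% significance level". It then says "The primary analysis will compare each dose group with placebo at Week 12" and names no multiplicity method. Under Secondary Endpoints Analyses, the same section says "Change from baseline in DAS28-CRP score at week 4, 8, 12 and 16 will be analyzed" from "LS-means calculated by MRMM model used in primary endpoint analysis without adjustment for multiplicity", and that list includes Week 12.

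SAP 4.11.1 writes three pairs of hypotheses, one per dose. "These hypotheses will be tested using a 2-sided 5% significance level", and "No adjustment for multiplicity will be performed for comparisons of each concentration of CPL409116 to placebo at week 12". There is no hierarchy among doses. A model that pools the three active arms is planned, but only as a sensitivity analysis.

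The Protocol synopsis counts the study a success if any one active arm is superior to placebo. This stands in a list introduced by "Following assumptions have been made for the purpose of sample size determination".

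**Remission and ACR.** Protocol 10.3 says that the proportion-test p-values for remission (Week 12) and for ACR response (Weeks 8 and 12) are adjusted for multiple comparisons. SAP 4.11.2 plans no correction for any secondary endpoint. The SAP introduction says that it reflects Protocol version 3.0 and does not mention the change.

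**The concern.** The Protocol gives an error rate for one claim, that some dose works. The SAP controls the error rate of three other claims, one per dose. With three chances to reject and no adjustment, the first rate must exceed the second. A reader who takes Protocol 10.3 at its word would treat a single significant dose as a 5% conclusion that the drug works, when the chance of reaching it falsely is about two and a half times that.

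For remission and ACR the two documents give opposite rules for the same p-values, so which results are called significant would depend on which document is followed.

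**Working it through.** **Inputs.** Three dose-versus-placebo tests, each two-sided at 5% (SAP 4.11.1). Allocation 1:1:1:1. 21 evaluable or 25 randomised per arm (Protocol 11.2 and synopsis). Week 12 difference 0.8, Week 12 SD 1.1, baseline SD 1.0 (Protocol 11.2). Residual degrees of freedom for an ANCOVA with four arms, baseline and five sites (the synopsis simulated up to five): 84 − 9 = 75, or 100 − 9 = 91.

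**1. The plan's own figure.** Each test taken alone has a 5% two-sided error rate, as SAP 4.11.1 says. The 5% reproduces per dose.

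**2. Correlation between the tests.** All three contrasts use the same placebo mean. Two contrasts have covariance σ²/n and each has variance 2σ²/n, so they correlate at 0.5.

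**3. Any-dose error if no dose works.** Conditioning on the standardised placebo mean x, with critical value c:

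- any two-sided rejection: 1 − ∫ φ(x) [Φ(x + c√2) − Φ(x − c√2)]³ dx
- at least one dose better: 1 − ∫ φ(x) [Φ(x + c√2)]³ dx

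For t-tests, c is multiplied by the estimated-to-true SD ratio and the result is averaged over its distribution.

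| Case | Any two-sided rejection | At least one dose better |
|---|---|---|
| Normal, c = 1.960 | 12.54% | 6.27% |
| t, 75 df (21 per arm) | 12.46% | 6.23% |
| t, 91 df (25 per arm) | 12.47% | 6.24% |
| Simulated ANCOVA, five sites, 21 per arm | 12.6–12.8% | 6.3–6.4% |
| Simulated ANCOVA, five sites, 25 per arm | 12.5% | 6.2–6.3% |

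Three independent tests would give 1 − 0.95³ = 14.3%; the shared placebo arm lowers this. The ratios to the stated level are 12.5/5 = 2.5 and 6.2/2.5 ≈ 2.5.

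**4. What would deliver 5%.** Dunnett's critical |t| is 2.40 at 75 df and 2.39 at 91 df, a per-test p of about 0.019. It gives 5.0% for any rejection and 2.5% in favour of a dose.

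**5. Remission and ACR.** The documents give no response rate and do not say whether the proportion test uses a continuity correction, so both are varied. The table shows the exact binomial chance of any false positive among three uncorrected dose tests, for one endpoint at one visit, as 21 / 25 per arm.

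| Common response | No continuity correction | With correction |
|---|---|---|
| 2% | 0.2% / 0.4% | 0.0% / 0.0% |
| 5% | 3.3% / 5.0% | 0.1% / 0.2% |
| 10% | 10.5% / 12.3% | 1.3% / 1.6% |
| 30% | 13.9% / 13.2% | 5.9% / 5.8% |
| 50% | 11.5% / 16.0% | 5.3% / 8.5% |

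The 16.0% is not all multiplicity: in that cell a single uncorrected test already has size 6.5%.

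**The case against.** The strongest reply is that the 5% in Protocol 10.3 can be read as the level at which each dose is declared different. The section goes on to per-dose comparisons, promises no adjustment for the primary tests, and lists Week 12 among the unadjusted DAS28-CRP contrasts. The SAP states the lack of adjustment openly, and the trial is described as proof of concept, where per-dose testing is common.

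Much of this stands. No promise on the primary tests was broken, each test holds its level, and the SAP makes no any-dose claim. But the per-dose reading is strained, because the Protocol sentence pairs a global null with an any-dose alternative before naming the level. Disclosing that nothing is adjusted does not tell the reader what the any-dose rate is. The pooled-arm model does not repair it, being a sensitivity analysis and not a gate.

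On the secondary endpoints, the Protocol's promise covers only remission at Week 12 and ACR at Weeks 8 and 12. SAP 4.11.2 also tests remission at any time and on Days 29, 57 and 113. The Protocol names neither a method nor the family of tests, and the size of the inflation is uncertain. These points limit what has to be restored. They do not remove the contradiction between the documents.

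**Conclusion.** The concern holds. The two-sided 5% in Protocol 10.3 is not the error rate of the planned procedure for the claim it is attached to. That rate is about 12.5%, or about 6.2% in favour of a dose against 2.5%. These figures assume that no dose works, that arms are of equal size and that all contrasts share one placebo arm; unequal final arm sizes would move them slightly. The error rate of each per-dose test is not in question.

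For remission and ACR, the Protocol and SAP conflict on the page. The inflation there depends on the response rate and the test version, and may be nil where responses are rare.

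**What to change.** Before unblinding:

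1. Reconcile Protocol 10.3 with SAP 4.11.1. State that 5% applies to each dose separately and that the any-dose error rate, if no dose works, is about 12.5% two-sided (about 6.2% in favour of a dose).
2. Report Dunnett-type adjusted p-values and simultaneous confidence intervals for the three Week 12 contrasts beside the unadjusted ones. SAP 4.11.1 already plans the step: "In order to compare each concentration of CPL409116 to placebo, LS means, their 95% CI, and p values will be calculated using" the emmeans function.
3. For remission at Week 12 and ACR at Weeks 8 and 12, restore the adjustment, naming the method and the family. Otherwise label the p-values nominal and record and justify the deviation, which Protocol section 10 requires in the CSR. State whether the proportion test uses a continuity correction.

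Items 1 and 2 cost a sentence and some output columns. The unadjusted tests stay primary, so no power is lost. Item 3 restores what the Protocol promised or adds a label.

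Making Dunnett the success criterion is optional and is not part of this fix. It would cost power. With 21 per arm and all three doses at −0.8, power for at least one dose falls from 86–92% to 73–83% (t contrasts), or from 84–91% to 70–81% (ANCOVA, five sites). With 25 evaluable per arm it falls from 91–96% to 81–89% (t contrasts). The ranges assume a baseline-to-Week-12 correlation r of 0 to 0.45, which the documents do not state. The upper value follows if the synopsis's combined SD of 1.1 is the SD of change: 1.1² = 1.0² + 1.1² − 2r(1.0)(1.1), so r = 1/2.2 = 0.45.

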2.2.2. Randomization and blinding

Both subjects and investigators will be blinded to treatment assignment using Interactive Web Response System (IWRS) system. A computer generated randomization schedule was prepared by Dicella Ltd. and subsequently uploaded to BIOSTAT Sp. z o. o. Electronic Data Capture system (EDC). The randomization is balanced by using randomly permuted blocks and stratified by age (with 57 years used as a cut-off). Investigator are able to break the blind for a given subject, in case of emergency, using tool provided within eCRF. Bioanalytical laboratory will be blinded until complete plasma CPL409116 and M3 metabolite concentrations table is provided to Clinical Department of Celon Pharma S.A.

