4.11.2. Secondary efficacy endpoints

No correction for multiple comparisons are planned for secondary endpoints.

Proportion of subjects with DAS28-CRP remission (score < 2.6) in each study arm will be presented at any time as well as at Day 29, Day 57, Day 85 and Day 113. Proportion of subjects will be presented together with confidence intervals, difference from placebo with confidence interval and p value for comparison vs. placebo calculated using proportion test. Logistic regression model will be prepared to explain achievement of response at any time with following factors: treatment (placebo will be the reference value), country (Ukraine will be the reference value) and baseline DAS28-CRP score. Moreover, descriptive statistics for time to remission will be presented along with median time to remission estimated using Kaplan-Meier method. Each treatment arm will be compared to placebo using log-rank test.

Change from baseline in the Tender/Painful and Swollen Joint Count as well as change from baseline in PhGA will be analyzed using MMRM and performed as described for primary endpoint.

All of patient reported outcomes - change from baseline in PAAP, PtGA, HAQ-DI, SF-36 and FACIT-F will be only presented descriptively for each timepoint.

American College Rheumatology (ACR)20, ACR50, ACR70 and ACR90 responder rates will be presented in form of percentage of subjects that meets the criteria for the endpoint alongside 95% confidence interval calculated using Wilsons' method. Difference between CPL409116 arms and placebo will be presented together with confidence interval and p value calculated using proportion test. Logistic regression model will be prepared similar to the previously described endpoint of DAS28-CRP remission.

Supportive analysis will be performed on PP population, as well as ITT with imputation based on last observation carried forward (LOCF) for continuous variables and NRI method for binary endpoints and performed as described for the ITT population.

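### The worded primary model leaves out age, the only stated stratification factor, and the SAP's sample R formula, which adds AGE and SEX, does not match the wording.

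*SAP*

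**What the plan says.** **Randomisation.** SAP 2.2.2 describes permuted blocks "stratified by age (with 57 years used as a cut-off" and names no other stratification factor. Protocol 4.1 also calls the randomisation age-stratified.

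**Worded models.** None contains age or sex.
- Protocol 1.1, Statistical Methods: "ANCOVA model with Baseline DAS28-CRP, clinical site (up to five sites were considered in simulation) and drug dose". Protocol 11.2 and SAP 2.3 list the same terms.
- Protocol 10.3: "with treatment, timepoint and clinical site as fixed effects and baseline score as a covariate".
- SAP 4.11.1: dose and timepoint, then "interaction between treatment and timepoint, clinical site, as well as baseline value of DAS28-CRP as continuous covariate".

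**Code.** SAP 4.11.1 follows its wording with an "R formula which could be used for such analysis", whose fixed part is "TREATMENT * TIMEPOINT + AGE + SEX + SITE + BASELINE". SAP 4.8 defines age both in continuous years and as <57/≥57. The formula does not say which one AGE is.

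**Other models.** Under sensitivity analysis, SAP 4.11.1 adds that "different formulation of the models will be explored (interactions between independent variables, simpler versions of the model". SAP 4.11.2 says that joint counts and PhGA "will be analyzed using MMRM and performed as described for primary endpoint".

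**The concern.** A factor used to balance the randomisation normally belongs in the primary model. Stratification removes between-arm variation due to age. A model without the stratum still counts that variation as residual error, so its standard error is too large whenever age predicts outcome.

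The second issue is consistency. The text and the code are offered as the same analysis but have different terms. If the wording governs, the stratification factor is missing. If the code governs, it adds a term of unstated form and a term the text never lists. The plan to explore simpler models does not help, because the worded model is itself a simpler version of the formula. Joint counts and PhGA inherit the mismatch.

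At stake are some precision and, in a small share of trials, which side of p = 0.05 a dose falls on. SAP 4.11.1 tests each dose at two-sided 5% without multiplicity adjustment, so each such p-value is read on its own.

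**Working it through.** **Inputs from the documents** (SAP 2.3, Protocol 11.2): 21 per arm, Week 12 SD 1.1, difference 0.8, power above 80%, dropout 16%, two-sided 5%.

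**Assumptions.** r is the correlation between age and outcome left after baseline and site. The documents give no value, so 0 and 0.3 are shown. The two age strata are equal in size. A Week 12 ANCOVA on complete data stands in for the MMRM. The simulations also assume blocks of 4, five sites and 75% women with no sex effect.

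**1. The plan's own figures.** Enrolment reproduces: 84/(1 − 0.16) = 100. For power, take 1.1 as the residual SD:
- SE = 1.1 × √(2/21) = 0.3395
- 0.8/0.3395 = 2.357
- power = Φ(2.357 − 1.960) = 65.4%, or about 62% in simulation with the site and baseline terms fitted.

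Power of 80% for one dose needs a residual SD of 0.8/[(1.960 + 0.842) × √(2/21)] ≈ 0.925. That corresponds to a baseline-to-Week-12 correlation of √(1 − (0.925/1.1)²) ≈ 0.54, which the documents do not state. So 0.925 is used for the disagreement rates below.

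**2. Precision lost by omitting the stratum at r = 0.3.** The ratio of standard errors does not depend on the SD.
- Linear age effect: a median split captures r × √(2/π) = 0.239, so the ratio is 1/√(1 − 0.239²) = 1.030.
- Step at 57: the ratio is 1/√(1 − 0.3²) = 1.048.

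Simulated mean SEs (10,000 trials, SD 1.1) agree: 0.3500/0.3397 = 1.030 (linear) and 0.3500/0.3335 = 1.049 (step).

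**3. Type I error of the worded model at r = 0.3.** The overstated SE moves the effective critical value from 1.960 to 1.960 × the ratio.
- Linear: 2 × [1 − Φ(2.019)] = 4.4%. Simulated 4.5%.
- Step: 2 × [1 − Φ(2.055)] = 4.0%. Simulated 4.2%.

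With the stratum included, the simulated value is 5.2% in both cases. The Monte Carlo SE is about 0.2 points.

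**4. How often the worded model and the formula (continuous AGE plus SEX) disagree on p < 0.05 for one dose, at a true difference of 0.8.**

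| Residual SD | r = 0 | r = 0.3 |
|---|---|---|
| 0.925 | about 3–4% | about 5–6% |
| 1.1 | 3.9–4.0% | 6.2–7.8% |

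Ranges cover the linear and step shapes. With no true difference, disagreement is 1 to 3% in the settings run.

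**5. Which form of age.** At r = 0.3, continuous age has an SE 1.5% smaller than the stratum if the effect is linear (0.3346 against 0.3397). It is 2.0% larger if the effect is a step at 57 (0.3403 against 0.3335). Neither is always better.

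**The case against.** The best reply is that the primary model is already settled. Every worded model agrees on leaving out age and sex. SAP 4.11.1 makes the worded model mandatory and offers the formula only as a possibility. The formula also uses TIMEPOINT in its fixed part and VISIT in its covariance part, which looks like a sketch rather than final code. This largely stands, and the wording has the better claim. It does not remove the mismatch, because the formula is presented as code for that same analysis. It also does not put the stratification factor into the model.

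A reader might go further and infer two or three equally pre-specified primary models, with the most favourable one chosen. The documents do not support that: text and code do not have equal standing, and SAP 4.8 makes continuous years a natural reading of AGE. Simulated best-of-three type I error is 5.4 to 6.6% per dose, at residual SD 1.1 and r from 0 to 0.5. It arises only if someone selects among models after unblinding, which the plan does not provide for.

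It is also fair to say that making text and code agree would by itself end the inconsistency, with or without the stratum. The reason for adding the stratum is that the trial stratified on it and that it costs almost nothing.

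The age and sex subgroups in SAP 3.2 do not answer the point. They are separate analyses and do not set the covariates of the primary model.

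**Conclusion.** The point holds and is small. As worded, the primary model omits the only stated stratification factor, and the SAP's sample code has different terms from its text.

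A reader might infer that the omission biases the treatment effect or inflates type I error. It does neither; the test becomes slightly conservative. At r = 0.3 the cost is a standard error about 3 to 5% larger and a type I error of about 4 to 4.5%. If age is unrelated to outcome, nothing is lost. The text-code mismatch changes the p < 0.05 verdict for a dose in about 3 to 4% of trials at r = 0 and 5 to 6% at r = 0.3, with residual SD near 0.925.

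All of these sizes rest on assumed values of r and on ANCOVA in place of the MMRM. The SD of 0.925 also assumes that the stated power refers to a single dose. If it means at least one of three doses, all with a true difference of 0.8, power is about 87% even at SD 1.1, and the second row of the table applies. The missing stratum and the mismatch themselves depend on none of this.

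**What to change.** Before unblinding, in SAP 4.11.1:
- State one binding primary model, identical in text and code: treatment, visit, treatment × visit, site, baseline DAS28-CRP and the randomisation age stratum (<57/≥57) as a factor.
- Put SEX in both text and code, or in neither.
- If a continuous-age version is wanted, name it as a sensitivity analysis among the alternative formulations.

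In SAP 4.11.2, say that the joint-count and PhGA models use the same terms, each with its own baseline. For the age subgroups in SAP 3.2, say that the stratum term is dropped, since it is constant within each subgroup.

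**Cost.** A few lines of text and no new data. The stratum uses one degree of freedom; if age is irrelevant, the simulated SE is about 0.1% larger (0.3498 against 0.3496). If the age effect is linear, the stratum recovers less precision than continuous age would.
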